**Confidential**

---

An additional consideration for sample size determination is the application of an inflation factor of 20% to account for drop-out rates during the Induction and Long Term Treatment Phases of the study. This consideration suggested that 330 subjects per treatment group would be required at study entry.

### **8.3 Analysis Populations**

#### **Intent-to-Treat (ITT) Population**

The ITT population will include all randomized subjects who take at least one dose of study drug.

**Per Protocol (PP) Population** will include all subjects in the ITT Population with the exception of those who failed to meet Inclusion Criteria 3 and 4; or met Exclusion Criteria 1, 2, 13 or 14.

The analyses of baseline characteristics and efficacy will be performed for the ITT Population. The primary efficacy analysis also will be performed on the PP Population as a sensitivity analysis. All safety analyses will be performed on the ITT Population.

### **8.4 Subject Disposition**

Subject disposition will be summarized by treatment and study phase and will include the number of subjects entered in the study; number and percentage of subjects who completed or prematurely discontinued (classified by reasons for premature discontinuation); the number of subjects entered in the study at each study site; and the number and percentage of subjects who completed or discontinued at each study site.

### **8.5 Demographic and Baseline Characteristics**

Demographic and baseline characteristics will be summarized descriptively by treatment group. Baseline will be defined as the last assessments prior to initiating the Treatment Period. The following demographic and baseline disease characteristics will be summarized:

#### **Demographics:**

- Age (years) = (date of informed consent signed – date of birth)/365.25;
- Age group (<65, >=65);
- Sex (male/female);
- Ethnicity (Hispanic or Latino/not Hispanic or Latino);
- Race (American Indian or Alaskan Native, Asian, Black or African-American, Native Hawaiian or Other Pacific Islander, White, and Other); subjects who identify more than one race will be categorized as “Other”;

- Height (cm);
- Weight (kg);
- Body mass index (kg/m^2) = (Weight in kg)/ (Height in m);
- Region (US/Rest Of World).

#### **Baseline characteristics:**

All baseline subject characteristics including demographic data (outlined above), baseline CDAI and SES-CD scores, duration of the disease (years), location of disease, previous steroid use (dose, duration), previous surgery for CD, smoking history (nonsmoker/ex-smoker/smoker), baseline CRP and fecal calprotectin values will be summarized by treatment arm. Baseline comparability will be assessed via descriptive measures, e.g., by comparing means, 95% confidence intervals and proportions.

### **8.6 Analysis Methods**

The phrases 'statistical analysis' or 'analysis' will be used to mean inferential analysis (such as performing tests of significance, reporting p-values and confidence intervals). When no inferential analysis will be performed, the phrases 'descriptive analysis' or 'descriptive statistics' will be used (for instance, producing summary tables of means, standard deviations, percentages of responders). All efficacy analyses will be conducted on ITT and PP populations. All efficacy analyses will adjust for country.

#### **8.6.1 Primary Efficacy Analysis,**

##### **Induction Phase**

There will be two co-primary measures of efficacy assessed during the Induction Phase. The first co-primary endpoint is:

- Clinical symptom remission defined by (1) the total number of liquid/very soft stools for the 7 days prior to the Week 16 visit being  $\leq 10$  (from CDAI Item 1); AND (2) an abdominal pain rating of  $\leq 1$  (from CDAI Item 2) on each day for the 7 days prior to the Week 16 visit.

The second co-primary endpoint is:

- Endoscopic response defined as a  $\geq 3$ -point decrease in the SES-CD from baseline to the SES-CD score obtained between Week 16 and Week 17. SES-CD scores will be calculated from centrally-read digital video of ileocolonoscopies performed at baseline and between Week 16 and Week 17.

For each endpoint, the null hypothesis  $H_0: \pi_R - \pi_P = 0$  versus the alternative  $H_A: \pi_R - \pi_P \neq 0$  is of interest, where  $\pi_R$  is the binomial parameter for induction of remission/response for the

Confidential

---

Rifaximin DR group, and  $\pi_P$  is the binomial parameter for induction of remission/response for the placebo group. Subjects who require the initiation of rescue medication and/or surgery for CD will be considered treatment failures from the date of the introduction of the rescue medication and/or surgery, regardless of their actual response data. The Cochran-Mantel-Haenszel (CMH) test, stratified by country, will be used to test the hypothesis. Each null hypothesis of no difference will be rejected if the resulting p-value for the respective statistical test is less than 0.05. Significance for the induction claim will only be declared if both null hypotheses are rejected. As such, the overall Type I error rate will be maintained at the 5% level without adjustment for multiple comparisons.

If it is evident that the response variable is confounded with some of the background variables, then logistic regression will be performed using the background variables as covariates. The differences between this adjusted analysis and the previous unadjusted analysis will be noted, and the impact of such differences will be discussed.

The primary efficacy analysis will be repeated on the PP population to assess the robustness of the results of the primary outcome.

### **Long Term Treatment Phase**

There will be two key co-secondary endpoints of efficacy assessed during the Long Term Treatment Phase. The first is:

- Clinical symptom remission defined by (1) the total number of liquid/very soft stools for the 7 days prior to the Week 52 visit being  $\leq 10$  (from CDAI Item 1); AND (2) an abdominal pain rating of  $\leq 1$  (from CDAI Item 2) on each day for the 7 days prior to the Week 52 visit.

The second is:

- Endoscopic remission defined as a SES-CD score of  $\leq 2$  at Week 52. SES-CD scores will be calculated from centrally-read digital video of ileocolonoscopies performed at Week 52.

For each endpoint, the number and proportion of subjects with clinical and endoscopic remission will be summarized by treatment group for the ITT Population.

For each endpoint, the null hypothesis  $H_0: \pi_R - \pi_P = 0$  versus the alternative  $H_A: \pi_R - \pi_P \neq 0$  is of interest, where  $\pi_R$  is the binomial parameter for remission for the Rifaximin DR group, and  $\pi_P$  is the binomial parameter for remission for the placebo group. Subjects who require the initiation of rescue medication and/or surgery for CD will be considered treatment failures from the date of the introduction of the rescue medication and/or surgery, regardless of their actual response data. The Cochran-Mantel-Haenszel (CMH) test, stratified by country, will be used to test the hypothesis. Each null hypothesis of no difference will be rejected if the resulting p-value for the respective statistical test is less than 0.05. Significance for clinical

Confidential

---

and endoscopic remission will only be declared if both null hypotheses are rejected. As such, the overall Type I error rate will be maintained at the 5% level without adjustment for multiple comparisons.

If it is evident that the response variable is confounded with some of the background variables, then logistic regression will be performed using the background variables as covariates. The differences between this adjusted analysis and the previous unadjusted analysis will be noted, and the impact of such differences will be discussed.

#### 8.6.2 Secondary Efficacy Analyses

Analysis of binary endpoints will be based on the methods outlined above for the primary efficacy analysis.

For time until durable response to the liquid/very soft stool component of the co-primary endpoint during the 52-Week Treatment Phase, a response will be considered durable if it started at Week 4 and lasted through Week 52. A response is defined as total number of liquid/very soft stools for the 7 days prior to the visit being  $\leq 10$  (from CDAI Item 1). The endpoint is then the time when the durable response began, or the first week of response that began the string of consecutive visits with response through Week 52. It is worth remarking that this endpoint would not be defined for a subject who does not have a durable response, so we consider instead the time of the last visit at which response was achieved. For example, if a subject is categorized as a responder at Week 52, then a durable response was not achieved. If a subject is categorized as a responder at Week 20, then a durable response started on Week 24. Time until durable response will be analyzed by the Kolmogorov-Smirnov test. Time until durable response to the abdominal pain component of the co-primary endpoint during the 52-Week Treatment Phase is analyzed similarly. A response is defined as abdominal pain rating of  $\leq 1$  (from CDAI Item 2) on each day for the 7 days prior to the visit.

Change from baseline in continuous outcomes (for example, the change from baseline in the SES-CD at Week 16) will be analyzed by fitting fixed effects linear models to the data. An initial model with terms for treatment, country, baseline, and baseline by treatment interaction will be fitted. The interaction term will be tested at a 0.10 level. A non-significant interaction will result in dropping the term from the model in subsequent analyses. If the final model involves heterogeneous slopes, then the analysis will include overall plots of baseline versus change from baseline by treatment groups, and plots of the estimated regression lines. Treatment differences will be estimated and tested at 25th, 50th and 75th percentiles of the baseline value.

Time to event data (for example, time to clinical remission) will be analyzed by Kaplan-Meier analysis (PROC LIEFTTEST in SAS/STAT) stratified by country. Additionally, the change from baseline in continuous outcomes measured at multiple post-baseline time points will be analyzed longitudinally using a mixed model. Models will include fixed effects for baseline

Confidential

---

value, country, treatment, week and the treatment by week interaction and allow for random subject effects. Treatment and week will each be fit as categorical variables. Models will be fit using SAS Proc Mixed assuming a compound symmetric correlation structure allowing for heterogeneous variances by week. The Kenward-Rogers approach for computing denominator degrees of freedom will be used to account appropriately for pooling of within- and between-subject variance estimates. Least squares means with 95% confidence intervals will be presented for each treatment\*week cross-classification. The basic SAS code will follow the structure below:

```
proc mixed;
class treatment country week subjectID;
model Y = baseline country treatment week treatment*week/ddfm=KenwardRoger solution;
random int/ subject=subjectID type =VC;
lsmeans treatment*week/stderr;
run;
```

Estimate and contrast statements will be included to compare the mean change from baseline averaged over all weeks for the treatment comparison.

To determine whether the declaration of response based on the co-primary endpoints for induction parallels the pattern of CDAI scores, Spearman correlation analyses will be applied to CDAI scores with the occurrence or non-occurrence of response based on the co-primary endpoints (Yes or No). Wilcoxon rank-sum test will be conducted to compare changes in the CDAI scores between responders and non-responders to the co-primary endpoints.

The Work Productivity and Activity Impairment Questionnaire: Crohn's disease (WPAI: CD) is an instrument with 6 questions that will be used to assess the effect of CD on subjects' work habits. A copy of the WPAI: CD questionnaire is provided in Appendix 6.

WPAI: CD outcomes are expressed as impairment percentages, with higher numbers indicating greater impairment and less productivity, i.e., worse outcomes. The four WPAI: CD outcome scores are computed as follows:

- % work time missed due to CD =  $100 * Q2 / (Q2 + Q4)$
- % impairment while working due to CD =  $100 * Q5 / 10$
- % overall work impairment =  $100 * [Q2 / (Q2 + Q4) + (1 - Q2 / (Q2 + Q4)) * (Q5 / 10)]$
- % activity impairment due to CD =  $100 * Q6 / 10$

The IBDQ Global Score is the sum of 32 responses, each ranging from 1 to 7, thus the Global Score ranges from 32 to 224; a higher score indicating a better quality of life. A copy of the IBDQ questionnaire is provided in Appendix 5.

**Confidential**

---

Changes from baseline in the four WPAI: CD and IBDQ Global Score outcomes will be analyzed by the methods outlined above for continuous outcomes.

#### **8.6.3 Safety Analyses**

Safety evaluations will be based on the incidence, intensity and types of AEs, and changes in vital signs, clinical laboratory results, physical exam and electrocardiograms. Concomitant medication, exposure to study medication and treatment compliance will be summarized descriptively.

#### **8.6.4 Extent of Exposure and Treatment Compliance**

The number of subjects administered study drug, the duration of exposure to study drug, and compliance data will be summarized descriptively.

#### **8.6.5 Adverse Events**

Adverse events will be coded using the Medical Dictionary for Regulatory Activities (MedDRA) coding dictionary. Treatment-emergent AEs will be defined as any event with a start date occurring on or after Visit 2 (Day 1) or, if pre-existing, worsening after Visit 2 (Day 1).

The incidence of treatment-emergent AEs will be summarized by body system and MedDRA preferred term. If a subject reports the same AE more than once, then that subject will only be counted once for the summary of that AE, using the most severe intensity.

Treatment-emergent AEs will be summarized as follows:

- All treatment-emergent AEs;
- All treatment-emergent AEs by intensity;
- All treatment-emergent AEs related to study drug;
- All treatment-emergent SAEs; and
- All treatment-emergent AEs that led to premature discontinuation of study drug.

#### **8.6.6 Clinical Laboratory Assessments**

Laboratory values will be summarized at baseline and at each time point. In addition, changes from baseline to last visit will be summarized.

A summary of shifts from baseline to final evaluation will be given for each treatment group for each parameter. The normal range for each parameter will be used to create categories of low, normal, or high. Any result higher than ULN or lower than the lower limit of normal (LLN) will be categorized as high or low respectively, and any result within the lower and

**Confidential**

---

upper limits of normal will be categorized as normal. The number and percentage of subjects in each treatment group in each shift category from baseline to final evaluation will be shown for each parameter.

All potentially clinically significant values for clinical laboratory tests will be assessed by the investigator. Out of range laboratory values that may be potentially clinically significant will be flagged for review.

#### **8.6.7 Vital Signs**

Vital sign measurements will be summarized at baseline and at each time point. In addition, changes from baseline to last visit in vital sign measurements will be summarized. For each summary the number, mean, median, standard deviation, minimum, and maximum values will be presented by treatment and study phase.

#### **8.6.8 Concomitant Medications**

Concomitant medications taken from screening and during the study will be categorized by World Health Organization (WHO) classification for therapeutic class and drug name and summarized by number and percentage of subjects.

#### **8.6.9 Physical Examinations**

Physical examination data will be presented in a data listing.

#### **8.6.10 Electrocardiogram**

ECG parameters will be summarized by treatment group using descriptive statistics. In order to assess the QT interval data, corrected QT (QTc) values will be calculated based on the following three methods.

1) Fridericia's correction:  $QTc = QT/RR^{0.33}$ ,

2) Bazett's Correction:  $QTc = QT/RR^{0.5}$ ,

And

3) Correction based on linear regression techniques: Based on the data from baseline study population, the intercept(a) and slope (b) will be estimated separately for males and females using the equation  $QT = a + b(1 - RR)$ . Those estimates will be used to calculate the corrected QT values at post baseline time points.

Confidential

---

QTc interval data at post-baseline visits will then be summarized descriptively by central tendency techniques. In addition, the frequency counts and percentages by treatment group for the following categories will be provided:

>450 with Baseline <=450,  
>480 with Baseline <=480,  
>500 with Baseline <=500,  
Increases from baseline > 30 and  
Increases from baseline > 60.

## 8.7 Statistical and Analytical Issues

### 8.7.1 Adjustment for Covariates

Efficacy analyses will be adjusted for country and baseline values.

### 8.7.2 Handling of Dropouts or Missing Data

Missing data will be handled using the Worst Case analysis method for the primary and key secondary endpoints. In the Worst Case analysis, subjects with fewer than 4 days of diary data in a given week will be considered non-responders for that week. Additionally, subjects with missing SES-CD data will be classified non-responder for that measure in that week.

The following three sensitivity analyses will be conducted to address the impact of missing data on the primary and key secondary endpoints:

**Last Observation Carried Forward (LOCF) Analysis:** In the first analysis, missing values will be replaced with the last previous non-missing value. The baseline values will not be carried forward.

**Multiple Imputation Analysis:** In the second analysis, missing values will be filled in by the multiple imputation method which involves the following distinct phases:

- The missing data will be filled in to generate complete data sets using SAS/STAT procedure PROC MI;
- The complete data sets will be analyzed using PROC LOGISTIC in SAS/STAT;
- The above two steps will be repeated 5 times;
- The results from the complete data sets will be combined for statistical inference using SAS/STAT procedure PROC MIANALYZE.

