7.10 Statistical and analytical issues

7.10.1 Handling of Dropouts or Missing Data

Missing data will be handled using the Worst-Case analysis method for the primary and key secondary endpoints. In the Worst-Case analysis, subjects with fewer than 4 days of diary data in a given week will be considered non-responders for that week. Additionally, subjects with missing SES-CD data will be classified non-responder for that measure in that week.

The following three sensitivity analyses will be conducted to address the impact of missing data on the primary and key secondary endpoints:

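### Five imputations with no stated seed leave the multiple-imputation check dependent on the seed when the result is near 0.05, and the SAP does not say whether it will be run

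*Protocol*

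**What the plan says.** Protocol 8.7.2 handles missing data on the primary and key secondary endpoints by a Worst Case rule and adds three sensitivity analyses: LOCF, multiple imputation and observed case. For multiple imputation, PROC MI fills in the data, then "The complete data sets will be analyzed using PROC LOGISTIC in SAS/STAT", then "The above two steps will be repeated 5 times", and the results are "combined for statistical inference using SAS/STAT procedure PROC MIANALYZE". No seed, imputation variables or logistic covariates are given.

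For the primary analysis in Protocol 8.6.1, "The Cochran-Mantel-Haenszel (CMH) test, stratified by country, will be used to test the hypothesis". Two general rules also apply: "All efficacy analyses will adjust for country" (Protocol 8.6) and "Efficacy analyses will be adjusted for country and baseline values" (Protocol 8.7.1).

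On the amount of missing data, Protocol 8.2 describes the "application of an inflation factor of 20% to account for drop-out rates during the Induction and Long Term Treatment Phases", giving 330 randomized per arm against about 240 needed at Week 16 and 210 at Week 52.

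SAP 7.10.1 states: "The following three sensitivity analyses will be conducted to address the impact of missing data on the primary and key secondary endpoints". Only LOCF follows, in 7.10.2; 7.10.3 turns to partial dates. SAP section 8 does not list multiple imputation among the analyses that will not be done.

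**The concern.** Multiple imputation adds random noise that shrinks as the number of imputations rises. With 5 imputations and a fifth to a third of outcomes missing, that noise can be large compared with the distance of a borderline result from 0.05. Without a stated seed, two programmers who follow the protocol exactly could report different conclusions from the same data.

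This check carries some weight. LOCF does not carry baseline forward, and endoscopy is scheduled only at baseline, Weeks 16–17 and Week 52. For Week 16 endoscopic response, LOCF therefore has nothing to carry unless an early-withdrawal endoscopy was obtained. The observed-case analysis drops subjects, and the protocol itself urges caution with it. Multiple imputation is then the only planned alternative to Worst Case that keeps every subject for that co-primary endpoint.

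**Working it through.** **Planning figures first.** For 40% against 55%, two-sided 0.05 and 240 per arm, power is 91.1%, which reproduces the stated 90% or more. On loss:
- The stated 20% gives 330 × 0.8 = 264 at Week 16.
- 240 of 330 implies 1 − 240/330 = 27.3% at Week 16.
- 210 of 330 implies 1 − 210/330 = 36.4% at Week 52. This matches 20% lost in each phase: 330 × 0.8 × 0.8 = 211.

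**Size of the noise.** Assumptions: 330 per arm, data missing at random, imputation within arm only, a treatment-only log odds ratio pooled by Rubin's rules, and observed rates close to 50% and 40%. With o subjects observed per arm:
- The within-imputation variance U is the sum over arms of 1/(330·p·(1−p)).
- The large-m total variance is about U × 330/o, so the between-imputation variance is B = U(330/o − 1).
- The SD of the pooled log odds ratio over seeds is √(B/m).

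| Missing | Responders / observed per arm | U | B | SD, m = 5 | SD, m = 100 | p as m grows |
|---|---|---|---|---|---|---|
| 20% | 132 v 106 / 264 | 0.0247 | 0.0062 | 0.035 | 0.008 | 0.023 |
| 27% | 120 v 96 / 240 | 0.0248 | 0.0093 | 0.043 | 0.010 | 0.028 |
| 36% | 106 v 84 / 211 | 0.0248 | 0.0140 | 0.053 | 0.012 | 0.032 |

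Example for the last row: the log odds ratio is ln(106/105) − ln(84/127) = 0.423. Its standard error is √(0.0248 × 330/211) = 0.197, so z = 2.15 and p = 0.032.

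B is itself estimated from only 5 values, which adds noise to the standard error and the degrees of freedom. Simulation over seeds on these fixed data sets captures both sources:

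| Missing | p, 5th–95th percentile, m = 5 | p, 5th–95th percentile, m = 100 |
|---|---|---|
| 20% | 0.008–0.078 | 0.018–0.030 |
| 27% | 0.008–0.113 | 0.021–0.037 |
| 36% | 0.007–0.150 | 0.023–0.044 |

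With 5 imputations, p < 0.05 occurs in about 67% of seeds at 27% missing and about 57% at 36%. With 100 it occurs in 99% at 36%. The mean 95% half-width on the log-odds scale at 36% missing is 0.418 with 5 and 0.387 with 100: 0.418/0.387 = 1.08, or 8% wider.

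These figures move with the data. At 105 v 84 of 210, the same arithmetic gives ln(1.5) = 0.405, standard error √(0.0248 × 330/210) = 0.197 and p = 0.040, which is closer to the line for any m.

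**At the planned effect.** For a fixed data set observed at about 55% against 40%, p ≥ 0.05 occurs with 5 imputations in 0%, 0.4% and 3% of seeds at 20%, 27% and 36% missing. Across simulated trials with those true rates, whose observed rates vary, two seeds disagree on significance in 5.0%, 8.7% and 13.3% of trials with 5 imputations. With 100 the figures are 0.7%, 0.8% and 1.6%.

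**The case against.** The strongest reply is that little depends on this. Success is decided by the CMH test under the Worst Case rule, and no decision rule is attached to the imputed p-value. The 10-point example is deliberately borderline; the plan expects 15 points. The wider interval is Rubin's rules allowing correctly for few imputations: a loss of efficiency, not an error. Baseline and earlier-visit predictors would reduce the between-imputation variance below the by-arm figures. Rescue and surgery cases count as failures, and endoscopy is sought from subjects who withdraw, so the share actually imputed may be below 20–36%. All of this stands and limits the size of the point. None of it supports keeping 5 imputations without a seed. The figure of 100 is partly judgement: with a large-m p-value near 0.03, 50 imputations already cut the share of seeds with p ≥ 0.05 to 0.4% at 20% missing and 6% at 36%, against 0% and 1% with 100.

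A reader might also infer more than the documents support:
- **That PROC LOGISTIC causes the seed dependence.** It does not; a CMH result pooled over 5 imputations would vary too.
- **That the logistic model omits country.** Protocol 8.7.2 lists no covariates at all, and 8.6 and 8.7.1 already require country adjustment. The gap is only that the covariates are not written out.
- **That the plan states 36% missing.** It states 20%; 27% and 36% are derived.
- **That the primary estimator is a Mantel-Haenszel risk difference.** Protocol 8.6.1 names a CMH test only.

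**Conclusion.** The point holds as a limited improvement to a sensitivity analysis. At the loss implied by the planning figures, 5 imputations without a seed make a near-threshold result irreproducible: at 36% missing, one data set gives p from 0.007 to 0.150 over the central 90% of seeds. At the planned effect a fixed data set seldom changes, and the primary test is untouched.

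The sizes assume 330 per arm, missingness at random, imputation by arm only and a 40% placebo rate. The Week 52 placebo rate is not given. SAP 7.3 says the studies will be terminated early, so the actual numbers will differ. Whether the analysis will be run at all is unclear from the SAP, and that should be settled first.

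**What to change.** 1. In SAP 7.10, either describe the multiple-imputation analysis in full or list it in section 8 as not performed.
2. If it is kept, replace the 5 repeats with at least 100 imputations under a pre-stated seed, in both Protocol 8.7.2 and the SAP.
3. Write out the imputation model: treatment, country, baseline and earlier visit values.
4. Separately, for comparability with the primary test, state that the PROC LOGISTIC step includes country, as the protocol already requires, or pool a country-stratified estimate instead.

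The cost is a few lines of text and negligible computing time. No new data are needed.
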